substantial. In addition, massive bleeding after cardiac surgery is associated with higher rates of reoperation, morbidity, and mortality.³ Current practice per our institutional transfusion algorithm is to use fresh frozen plasma as first line therapy for factor mediated coagulopathy and bleeding after cardiopulmonary bypass.

Large prospective randomized studies directly comparing PCC to FFP in the setting of factor-mediated bleeding after cardiac surgery have not been conducted.

We hypothesize that PCC use will show a reduction in allogenic transfusion requirements in cardiac surgical patients with factor mediated postcardiopulmonary bypass bleeding.

2. Specific Aims:

Our aim is to conduct a prospective randomized controlled trial of patients undergoing elective cardiac surgery. We plan to preoperatively consent and enroll sufficient patients to reach a goal of 200 randomized patients (100 patients per arm) that demonstrate clinically significant microvascular bleeding and factor mediated coagulopathy after cardiopulmonary bypass. Randomized patients with clinically significant factor mediated bleeding will receive transfusion of PCC (Kcentra) (100 patients) or fresh frozen plasma (100 patients). Factor mediated coagulopathy will be defined per our current transfusion algorithm as PT >16.6 sec/ INR >1.6 sec. Primary outcome measures for efficacy will be total units of allogenic blood product transfused, and 24 hour postoperative blood loss. Outcome measure for safety will be rate of serious adverse outcomes. Analysis of coagulation factor levels will also be conducted prior to cardiopulmonary bypass, post cardiopulmonary bypass, and after product administration (PCC or FFP).

Hypothesis:

PCC arm will have same or decreased allogenic blood product transfusion rate and blood loss after cardiac surgery compared to patients receiving fresh frozen plasma.

3. Research Design and Methods:

A. Study Overview

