The primary adverse event of concern in this study would be thromboembolic events. DSMB (anesthesiologist, hematologist, and statistician) will meet quarterly, and review all data from each study arm. Thromboembolic complications will be reviewed and clinical judgment will used to determine necessity of study termination. No formal stopping rules are feasible given the study size and low incidence of TEE.

Early termination of the study will ensue if adverse events in either study arm exceed acceptable level.

D. Randomization and Blinding

Upon consent for study participation enrolled patients will be randomized via computer-generated blocks and with stratification according to the surgical procedure to either receive PCC or FFP during cardiac surgery should they develop excessive microvascular bleeding in the

surgical field as determined by the surgical team in addition to a PT >16.6 sec/ INR >1.6 sec after cardiopulmonary bypass. The randomization assignments will be concealed in opaque envelopes and disclosed to the anesthesiologist caring for the patient. The surgical and intensive care personnel will not be blinded to the treatment arm, as transparency of transfusion product is necessary to prevent overdosage of PCC and potential thrombotic complications.

E. Interventions

Patients will be consented and enrolled in the study until 50 patients have received treatment in each arm of the study. Patients will be anticoagulated according to institutional practice with heparin 400 units/kg with goal ACT >400 prior to initiation of cardiopulmonary bypass. After cardiopulmonary bypass, patients will receive protamine at dose 0.01 mg/unit of heparin given with target ACT within 10% of baseline value. After protamine administration the ACT, CBC, PT/ INR, and fibrinogen, will be collected via preexisting arterial access. If ACT >10% baseline additional protamine will be given at the anesthesiologists discretion. Evaluation and determination of excessive microvascular bleeding in the surgical field will occur 10 minutes after return of ACT to within 10% of baseline. Patients with clinical evidence of excessive microvascular bleeding in the surgical field as determined by the surgical team, along with a PT >16.6 sec/ INR >1.6 sec will receive randomized treatment with either PCC or FFP.

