Power Analysis was determined from a study by Arnekian et al that retrospectively presented a reduction in blood loss in patients receiving PCC over those receiving FFP.² In that study, the distribution of 24-hr chest tube drainage was highly skewed, but the observed difference between the two groups was at least 0.65 standard deviation units. Using a non-parametric test, a sample-size of **N=50 per group should provide statistical power of >85% to detect a difference of this magnitude. Therefore we suggest a sample-size of at least 50 per group.** In the paper, they also found a dramatic difference in ICU red cell transfusions. If the true difference is as large as they observed a sample-size of N=50 per group would also provide adequate statistical power for this endpoint.²

Primary endpoints in this study will be units of allogenic blood product administration, and 24 hour postoperative blood loss. Exploratory endpoints will include rate of serious adverse outcomes.

Baseline patient characteristics, including demographics, comorbidities, preoperative laboratory values, and cardiovascular variables will be reported and compared across treatment groups. Categorical variables will be reported as counts and percentages, and compared across groups using chi-square or Fisher's exact tests. Continuous variables will be reported as median and interquartile ranges, and compared across groups using Wilcoxon rank sum tests.

K. Feasibility and Time Frame

This study with the combined collaboration of divisions of anesthesiology and cardiovascular surgery is quite feasible. Approximately 2200-2500 cardiopulmonary bypass procedures are done annually at St. Mary's Hospital. Making the conservative estimate that 50% will consent 1000 patients should be consented within 1 year. Given that approximately 11% of patients

receive transfusion; this would result in approximately 100-110 patients to be treated within 12 months. We expect to get IRB approval within the next one month. The study and data collection will take about 1 year with approximately two months for data analysis.

L. Strengths and Limitations

Strengths: This will be the first prospective randomized controlled trial in the United States directly assessing the effect of PCC compared to FFP in the setting of postcardiac surgery coagulopathy and bleeding in patients undergoing elective cardiac surgery.

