Limitations: If the study demonstrates lower transfusion requirements and blood loss in the PCC arm, further studies will need to address optimal dosing requirements. Current PCC dosing is based on INR and weight for patients on warfarin therapy. Should no difference be found between groups, or lower transfusion rate and/or postsurgical blood loss is found in the FFP arm, the question as to whether this represents a superior result of FFP or underdosing of the PCC arm will remain.

M. Anticipated Results

- a. PCC administration will reduce the amount of allogenic blood product transfused and amount of postoperative bleeding in patients undergoing cardiac surgery.
- b. Adverse event rate will be similar between the 2 treatment arms, representing the known risk associated with cardiovascular surgery.
- c. Perioperative transfusion related costs will be similar or lower in patients receiving PCC compared with FFP

N. Estimated Costs

Kcentra will be supplied and funded by CSL Behring (Melbourne, Australia). FFP if administered will be covered by the patient/payer as this treatment is the current practice standard. All laboratory testing not routine to this patient population will be funded by CSL Behring and is outline within the budget.

O. Research Materials

All data forms will be stored in individual patients study folders and handled securely for patient confidentiality. This data will be entered into an access database that is password protected.

P. Human Subjects

We will obtain informed consent from all participants prior to initiation of the study. Informed consent will meet the requirements of the code of federal regulations 21CFR 50.25 (elements of informed consent) and the IRB of this center. During informed consent for the study cardiac

surgical patients will be told that the chance of needing a transfusion in the perioperative period is around 11%. Should they meet criteria by our current transfusion algorithm to receive FFP, they would have been randomized to receive either FFP or the study PCC infusion. A copy of the consent form will be placed in the patient's medical records. The study will be stopped when 50 patients have received treatment in each study arm. Efficacy will be defined as either a statistically significant reduction in transfusion of allogenic blood products or 24 hour postoperative blood loss. Safety will be defined as similar rate of serious adverse outcomes in the PCC study drug arm to the standard therapy FFP arm.

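### Section P defines safety as a similar serious adverse outcome rate without a margin or test, and 50 per arm is too few to support that conclusion at low or moderate event rates

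*Combined protocol and SAP*

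**What the plan says.** Section P (Human Subjects) gives two success criteria in consecutive sentences. For efficacy: "Efficacy will be defined as either a statistically significant reduction in transfusion of allogenic blood products or 24 hour postoperative blood loss". For safety: "Safety will be defined as similar rate of serious adverse outcomes in the PCC study drug arm to the standard therapy FFP arm". The same section fixes the size: "The study will be stopped when 50 patients have received treatment in each study arm".

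Other parts of the protocol bear on the safety criterion:

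- Section J (Statistics/Power Analysis) gives the outcome a lower status: "Exploratory endpoints will include rate of serious adverse outcomes". Its quantified power statement concerns 24-hour chest tube drainage, with an unquantified remark on ICU red cell transfusion. It has no power statement for safety.
- Section C (Enrollment) names thromboembolic events as the adverse event of most concern, and then states: "No formal stopping rules are feasible given the study size and low incidence of TEE".
- Section G (Data Collection) lists the serious adverse events counted to 30 days. They are thromboembolic events (including myocardial infarction, stroke and death from any cause), new dialysis, ARDS and transfusion reactions. Thromboembolic events are found on clinical suspicion, without screening.
- Section M (Anticipated Results) expects adverse event rates to be alike in the two arms.

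No section gives a margin, a confidence limit, an expected event rate or a test for the serious adverse outcome comparison.

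**The concern.** The safety sentence is worded as a rule for drawing a conclusion, and it stands beside the efficacy rule. Anyone following it would report PCC as safe if the two rates were judged alike, yet nothing says how alike they must be or how that is to be shown. With few events, a wide range of true differences is compatible with rates that do not differ significantly. A positive safety statement about a procoagulant could then rest on a comparison that carries little information. Calling the outcome exploratory in Section J does not remove the problem, because Section P still allows the conclusion.

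**Working it through.** **Inputs from the documents.** 50 treated per arm (Sections C, E, J and P); a standardised difference of 0.65 and stated power above 85% (Section J).

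**Assumed inputs.** Two-sided alpha of 0.05, which is not stated. FFP serious adverse outcome rates of 2% to 30%, since none is given. Fisher's exact or chi-square test: Section J names these in its paragraph on baseline characteristics and assigns no test to serious adverse outcomes.

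**1. The plan's own figure.** Section J says "the observed difference between the two groups was at least 0.65 standard deviation units" and "N=50 per group should provide statistical power of >85% to detect a difference of this magnitude". By the normal approximation, power = Φ(0.65·√(n/2) − 1.96).

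- n = 50: Φ(3.25 − 1.96) = 90.1%.
- Wilcoxon efficiency 0.955 (normal data), effective n = 47.75: 88.8%.
- Worst-case efficiency 0.864, effective n = 43.2: 85.6% (84.8% with the noncentral t).

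The stated figure reproduces in substance. It concerns blood loss only.

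**2. Power to detect a true doubling of serious adverse outcomes, 50 per arm.** For each pair of rates, the binomial probabilities of all outcomes with p < 0.05 were summed.

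| FFP vs PCC rate | Fisher | Chi-square |
|---|---|---|
| 2% vs 4% | 0.6% | 5.2% |
| 5% vs 10% | 6.3% | 14.3% |
| 10% vs 20% | 19.5% | 30.2% |
| 15% vs 30% | 35.4% | 44.2% |
| 20% vs 40% | 51.5% | 59.5% |
| 25% vs 50% | 67.5% | 74.5% |
| 30% vs 60% | 82.9% | 87.6% |

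Power reaches 50% at an FFP rate of about 17% (chi-square) or 19.5% (Fisher). For 80% power by the usual two-proportion formula, a doubling from 5%, 10% or 15% needs 435, 199 or 121 per arm.

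**3. Precision when the true rates are equal.** The 95% half-width is 1.96·√(2p(1 − p)/50).

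- p = 5%: 1.96·√0.0019 = 8.5 points.
- p = 10%: 1.96·√0.0036 = 11.8 points.
- p = 20%: 1.96·√0.0064 = 15.7 points.

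The chance that the upper limit excludes a doubling is Φ(p/√(2p(1 − p)/50) − 1.96). This is 21% at p = 5%, 39% at 10%, 71% at 20% and 82% at 25%.

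**4. An example.** Observed counts of 5/50 on FFP and 10/50 on PCC give Fisher p = 0.26. The upper 95% limit for the difference is about 24 points.

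**5. The other reading of *similar*.** Suppose it means that the observed counts look close, for instance an excess of at most 2 PCC events. A true doubling would pass with probability 51% at 5% vs 10%, 24% at 10% vs 20%, and 5% at 20% vs 40%. The cut-off of 2 events is only an illustration. The result depends on a threshold that the plan does not set.

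**The case against.** A reader might infer that a real doubling of harm would usually be declared safe, or that 50 per arm can never show similarity. The documents support neither statement without conditions.

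- **Meaning of *similar*.** No section equates it with a non-significant result. The efficacy sentence uses significance language and the safety sentence does not. On the looks-close reading in step 5, a doubling from 10% would usually not pass.
- **Event rate.** The remark on low incidence concerns thromboembolic events. The safety outcome is broader and its rate is not stated. Above about 17–20% on FFP, a doubling would be detected more often than not.
- **Choice of test.** Fisher's test gives the lowest power. Chi-square gives 14% rather than 6% at 5% vs 10%, and 30% rather than 20% at 10% vs 20%.
- **Margin.** With a 2% rate in both arms and an illustrative 10-point margin, 31 per arm would give 80% power for non-inferiority (Wald formula, one-sided 0.025). The same margin needs 75 per arm at 5% and 142 at 10%.
- **Sample size.** Section 2 (Specific Aims) states a "goal of 200 randomized patients (100 patients per arm"), in conflict with the 50 used elsewhere. At 100 per arm, power for a doubling (normal approximation) would be 27% at 5%, 51% at 10% and 72% at 15%.
- **Oversight.** The DSMB reviews data by arm, outcome events are adjudicated blind to assignment, and Section C's remark on feasibility concerns stopping rules rather than the final comparison.

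All of this stands, and it makes the size of the problem conditional. It does not supply the missing criterion. If *similar* does not mean non-significant, its meaning is left open until the data are known. DSMB review protects patients during the trial but does not govern what the final report may conclude.

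**Conclusion.** The concern holds in conditional form. Section P sets a safety conclusion that has no margin, confidence limit or test, rests on a sample sized for efficacy, and does not fit the exploratory label in Section J. This goes beyond missing detail, because following the sentence permits a positive safety claim from a comparison that may say little.

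For FFP rates of 2% to 15%, most trials of this size would miss a true doubling at the 5% level: power is at most 35% (Fisher) or 44% (chi-square). Calling a non-significant result safe would then be wrong more often than not when harm is in fact doubled. That statement rests on the assumed rates, two-sided 0.05, and the reading of *similar* as not significantly different. Thromboembolism, the stated main concern, is described as infrequent, which puts it where power is lowest. If the composite rate on FFP is above about 20%, the power argument weakens, but the criterion remains undefined.

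**What to change.** Replace the safety sentence in Section P with: *Serious adverse event and thromboembolic event rates will be reported by arm with the risk difference and its 95% confidence interval, as exploratory outcomes. A non-significant difference will not be interpreted as similarity or safety; the upper confidence limit will be reported as the excess risk not excluded.*

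This brings Section P into line with Section J. Section 2 and Section H (Outcomes) only name the safety outcome and need no change on this point. The change is to wording alone: it needs no further patients and no new data. What is given up is a stronger safety claim, which the sample could not support at low or moderate event rates.

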I am contacting you to ask you some questions in regard to the research study that we are doing here at the Mayo Clinic involving people who have had heart surgery. You had provided consent to participate in this study prior to your heart surgery. Please understand that your current care and future care at the Mayo Clinic will not be affected by whether or not you participate. Specifically, your care will not be jeopardized if you choose not to answer the questions. Would you be willing to answer some questions regarding your surgery?

If yes: Is now a good time or would you like me to call you back?

If no: Thank you for your time.

1. Have you seen a doctor for any reason since being discharged from the hospital after your surgery?

If yes: Could you please tell me the reason.

If no: go to question 2

2. Have there been any changes in your health status since being discharged from the hospital after your heart surgery?

If yes: document

If no: go to question 3

3. Have you had any problems specifically with blood clots, heart attack, stroke, or damage to your kidneys requiring dialysis?

If yes: document

*****If the participant you wish to speak with is not available, ask:** When would it be a good time to call to speak with _____? Thank you, I will return the call at that time.

*****If there is any indication that the patient is deceased:** I'm truly sorry to hear that. Mr/Mrs _____ agreed to participate in a study concerning his/her recent

heart surgery. If you are willing to answer some questions, we may be able to collect some information that is helpful to the study. Would you be willing to share the circumstances of Mr/Mrs _____ death?

If yes: document. If not stated by call recipient, pose question number three phrased for a third party.

If no: I can certainly understand. Thank you very much for your time. (end call)

Closing: Thank you for participating in our research study. Please understand that your answers to the questions will be kept confidential and when the data from this research study is reported your data will be included in a summary without your name or any other identifying information.
